Appendix A: Results Tables.

Table A1: Primary outcome and confirmatory secondary outcomes with ordered testing procedure per comparison. Analyses from the prespecified multiply imputed analysis.

| | A: Est [95% CI] | B: Est [95% CI] | C: Est [95% CI] | AvC: Est [95% CI] | AvC p-value | BvC: Est [95% CI] | BvC p-value |
|------------------------|-----------------|-----------------|-----------------|-------------------|-------------|-------------------|-------------|
| PP glucose AUC | NA [NA; NA] | NA [NA; NA] | NA [NA; NA] | NA [NA; NA] | NA | NA [NA; NA] | NA |
| PP insulin AUC | NA [NA; NA] | NA [NA; NA] | NA [NA; NA] | NA [NA; NA] | * | NA [NA; NA] | * |
| Fasting insulin | NA [NA; NA] | NA [NA; NA] | NA [NA; NA] | NA [NA; NA] | * | NA [NA; NA] | * |
| Fasting glucose | NA [NA; NA] | NA [NA; NA] | NA [NA; NA] | NA [NA; NA] | * | NA [NA; NA] | * |
| HbA1c | NA [NA; NA] | NA [NA; NA] | NA [NA; NA] | NA [NA; NA] | * | NA [NA; NA] | * |

Table A2: Best-worst case sensitivity analysis of the primary analysis.

| | A: Est [95% CI] | B: Est [95% CI] | C: Est [95% CI] | AvC: Est [95% CI] | BvC: Est [95% CI] |
|------------------------|-----------------|-----------------|-----------------|-------------------|-------------------|
| PP glucose AUC | NA [NA; NA] | NA [NA; NA] | NA [NA; NA] | NA [NA; NA] | NA [NA; NA] |
| PP insulin AUC | NA [NA; NA] | NA [NA; NA] | NA [NA; NA] | NA [NA; NA] | NA [NA; NA] |
| Fasting insulin | NA [NA; NA] | NA [NA; NA] | NA [NA; NA] | NA [NA; NA] | NA [NA; NA] |
| Fasting glucose | NA [NA; NA] | NA [NA; NA] | NA [NA; NA] | NA [NA; NA] | NA [NA; NA] |
| HbA1c | NA [NA; NA] | NA [NA; NA] | NA [NA; NA] | NA [NA; NA] | NA [NA; NA] |

Table A3: Complete case sensitivity analysis of the primary analysis.

| | A: Est [95% CI] | B: Est [95% CI] | C: Est [95% CI] | AvC: Est [95% CI] | BvC: Est [95% CI] |
|------------------------|-----------------|-----------------|-----------------|-------------------|-------------------|
| PP glucose AUC | NA [NA; NA] | NA [NA; NA] | NA [NA; NA] | NA [NA; NA] | NA [NA; NA] |
| PP insulin AUC | NA [NA; NA] | NA [NA; NA] | NA [NA; NA] | NA [NA; NA] | NA [NA; NA] |
| Fasting insulin | NA [NA; NA] | NA [NA; NA] | NA [NA; NA] | NA [NA; NA] | NA [NA; NA] |
| Fasting glucose | NA [NA; NA] | NA [NA; NA] | NA [NA; NA] | NA [NA; NA] | NA [NA; NA] |
| HbA1c | NA [NA; NA] | NA [NA; NA] | NA [NA; NA] | NA [NA; NA] | NA [NA; NA] |

Table A4: Exploratory outcome analyses for outcomes used in the multiple imputation of the primary outcome, ie using the imputed data.

| | A: Est [95% CI] | B: Est [95% CI] | C: Est [95% CI] | AvC: Est [95% CI] | AvC p-value | BvC: Est [95% CI] | BvC p-value |
|---------------------------|------------------------|------------------------|------------------------|--------------------------|--------------------|--------------------------|--------------------|
| Glucose.auc.break | NA [NA; NA] | NA [NA; NA] | NA [NA; NA] | NA [NA; NA] | NA | NA [NA; NA] | NA |
| Glucose.auc.lunch | NA [NA; NA] | NA [NA; NA] | NA [NA; NA] | NA [NA; NA] | NA | NA [NA; NA] | NA |
| Glucose.auc.dinner | NA [NA; NA] | NA [NA; NA] | NA [NA; NA] | NA [NA; NA] | NA | NA [NA; NA] | NA |
| Insulin.auc.break | NA [NA; NA] | NA [NA; NA] | NA [NA; NA] | NA [NA; NA] | NA | NA [NA; NA] | NA |
| Insulin.auc.lunch | NA [NA; NA] | NA [NA; NA] | NA [NA; NA] | NA [NA; NA] | NA | NA [NA; NA] | NA |
| Insulin.auc.dinner | NA [NA; NA] | NA [NA; NA] | NA [NA; NA] | NA [NA; NA] | NA | NA [NA; NA] | NA |
| Weight | NA [NA; NA] | NA [NA; NA] | NA [NA; NA] | NA [NA; NA] | NA | NA [NA; NA] | NA |

Table A5: Exploratory outcome analyses for outcomes not used in the multiple imputation of the primary outcome, ie complete case analyses.

| | A: Est [95% CI] | B: Est [95% CI] | C: Est [95% CI] | AvC: Est [95% CI] | AvC p-value | BvC: Est [95% CI] | BvC p-value |
|----------------------------------|------------------------|------------------------|------------------------|--------------------------|--------------------|--------------------------|--------------------|
| Mean Glucose CGM | NA [NA; NA] | NA [NA; NA] | NA [NA; NA] | NA [NA; NA] | NA | NA [NA; NA] | NA |
| iAUC glucose CGM | NA [NA; NA] | NA [NA; NA] | NA [NA; NA] | NA [NA; NA] | NA | NA [NA; NA] | NA |
| Nocturnal glucose CGM | NA [NA; NA] | NA [NA; NA] | NA [NA; NA] | NA [NA; NA] | NA | NA [NA; NA] | NA |
| CGM time below range | NA [NA; NA] | NA [NA; NA] | NA [NA; NA] | NA [NA; NA] | NA | NA [NA; NA] | NA |
| CGM time in range | NA [NA; NA] | NA [NA; NA] | NA [NA; NA] | NA [NA; NA] | NA | NA [NA; NA] | NA |
| CGM time above range | NA [NA; NA] | NA [NA; NA] | NA [NA; NA] | NA [NA; NA] | NA | NA [NA; NA] | NA |
| MAGE | NA [NA; NA] | NA [NA; NA] | NA [NA; NA] | NA [NA; NA] | NA | NA [NA; NA] | NA |
| MODD | NA [NA; NA] | NA [NA; NA] | NA [NA; NA] | NA [NA; NA] | NA | NA [NA; NA] | NA |
| Insulin secretion rate | NA [NA; NA] | NA [NA; NA] | NA [NA; NA] | NA [NA; NA] | NA | NA [NA; NA] | NA |
| Insulin sensitivity index | NA [NA; NA] | NA [NA; NA] | NA [NA; NA] | NA [NA; NA] | NA | NA [NA; NA] | NA |
| HOMA-IR | NA [NA; NA] | NA [NA; NA] | NA [NA; NA] | NA [NA; NA] | NA | NA [NA; NA] | NA |
| Fasting C-peptide | NA [NA; NA] | NA [NA; NA] | NA [NA; NA] | NA [NA; NA] | NA | NA [NA; NA] | NA |
| Fasting Triglycerides | NA [NA; NA] | NA [NA; NA] | NA [NA; NA] | NA [NA; NA] | NA | NA [NA; NA] | NA |
| Fasting free fatty acids | NA [NA; NA] | NA [NA; NA] | NA [NA; NA] | NA [NA; NA] | NA | NA [NA; NA] | NA |
| Trigs AUC of 3 meals | NA [NA; NA] | NA [NA; NA] | NA [NA; NA] | NA [NA; NA] | NA | NA [NA; NA] | NA |
| Trigs AUC of breakfast | NA [NA; NA] | NA [NA; NA] | NA [NA; NA] | NA [NA; NA] | NA | NA [NA; NA] | NA |
| Trigs AUC of lunch | NA [NA; NA] | NA [NA; NA] | NA [NA; NA] | NA [NA; NA] | NA | NA [NA; NA] | NA |
| Trigs AUC of dinner | NA [NA; NA] | NA [NA; NA] | NA [NA; NA] | NA [NA; NA] | NA | NA [NA; NA] | NA |
| FFA AUC of 3 meals | NA [NA; NA] | NA [NA; NA] | NA [NA; NA] | NA [NA; NA] | NA | NA [NA; NA] | NA |
| FFA AUC of breakfast | NA [NA; NA] | NA [NA; NA] | NA [NA; NA] | NA [NA; NA] | NA | NA [NA; NA] | NA |

| | | | | | | | |
|-------------------------------|-------------|-------------|-------------|-------------|----|-------------|----|
| FFA AUC of lunch | NA [NA; NA] | NA [NA; NA] | NA [NA; NA] | NA [NA; NA] | NA | NA [NA; NA] | NA |
| FFA AUC of dinner | NA [NA; NA] | NA [NA; NA] | NA [NA; NA] | NA [NA; NA] | NA | NA [NA; NA] | NA |
| Systolic BP | NA [NA; NA] | NA [NA; NA] | NA [NA; NA] | NA [NA; NA] | NA | NA [NA; NA] | NA |
| Diastolic BP | NA [NA; NA] | NA [NA; NA] | NA [NA; NA] | NA [NA; NA] | NA | NA [NA; NA] | NA |
| Total cholesterol | NA [NA; NA] | NA [NA; NA] | NA [NA; NA] | NA [NA; NA] | NA | NA [NA; NA] | NA |
| HDL | NA [NA; NA] | NA [NA; NA] | NA [NA; NA] | NA [NA; NA] | NA | NA [NA; NA] | NA |
| LDL | NA [NA; NA] | NA [NA; NA] | NA [NA; NA] | NA [NA; NA] | NA | NA [NA; NA] | NA |
| C-reactive protein | NA [NA; NA] | NA [NA; NA] | NA [NA; NA] | NA [NA; NA] | NA | NA [NA; NA] | NA |
| BMI | NA [NA; NA] | NA [NA; NA] | NA [NA; NA] | NA [NA; NA] | NA | NA [NA; NA] | NA |
| Sleep duration | NA [NA; NA] | NA [NA; NA] | NA [NA; NA] | NA [NA; NA] | NA | NA [NA; NA] | NA |
| Arousals | NA [NA; NA] | NA [NA; NA] | NA [NA; NA] | NA [NA; NA] | NA | NA [NA; NA] | NA |
| AHI | NA [NA; NA] | NA [NA; NA] | NA [NA; NA] | NA [NA; NA] | NA | NA [NA; NA] | NA |
| Light sleep | NA [NA; NA] | NA [NA; NA] | NA [NA; NA] | NA [NA; NA] | NA | NA [NA; NA] | NA |
| Deep sleep | NA [NA; NA] | NA [NA; NA] | NA [NA; NA] | NA [NA; NA] | NA | NA [NA; NA] | NA |
| REM sleep | NA [NA; NA] | NA [NA; NA] | NA [NA; NA] | NA [NA; NA] | NA | NA [NA; NA] | NA |
| Sleep latency | NA [NA; NA] | NA [NA; NA] | NA [NA; NA] | NA [NA; NA] | NA | NA [NA; NA] | NA |
| Sitting time | NA [NA; NA] | NA [NA; NA] | NA [NA; NA] | NA [NA; NA] | NA | NA [NA; NA] | NA |
| Standing time | NA [NA; NA] | NA [NA; NA] | NA [NA; NA] | NA [NA; NA] | NA | NA [NA; NA] | NA |
| Stepping time | NA [NA; NA] | NA [NA; NA] | NA [NA; NA] | NA [NA; NA] | NA | NA [NA; NA] | NA |
| Mean daily steps | NA [NA; NA] | NA [NA; NA] | NA [NA; NA] | NA [NA; NA] | NA | NA [NA; NA] | NA |
| Adherence | NA [NA; NA] | NA [NA; NA] | NA [NA; NA] | NA [NA; NA] | NA | NA [NA; NA] | NA |
| Eating window | NA [NA; NA] | NA [NA; NA] | NA [NA; NA] | NA [NA; NA] | NA | NA [NA; NA] | NA |
| 95% Eating window | NA [NA; NA] | NA [NA; NA] | NA [NA; NA] | NA [NA; NA] | NA | NA [NA; NA] | NA |
| Protein | NA [NA; NA] | NA [NA; NA] | NA [NA; NA] | NA [NA; NA] | NA | NA [NA; NA] | NA |
| Carbohydrate | NA [NA; NA] | NA [NA; NA] | NA [NA; NA] | NA [NA; NA] | NA | NA [NA; NA] | NA |
| Fat | NA [NA; NA] | NA [NA; NA] | NA [NA; NA] | NA [NA; NA] | NA | NA [NA; NA] | NA |
| Sat fat | NA [NA; NA] | NA [NA; NA] | NA [NA; NA] | NA [NA; NA] | NA | NA [NA; NA] | NA |
| Fibre | NA [NA; NA] | NA [NA; NA] | NA [NA; NA] | NA [NA; NA] | NA | NA [NA; NA] | NA |
| Alcohol | NA [NA; NA] | NA [NA; NA] | NA [NA; NA] | NA [NA; NA] | NA | NA [NA; NA] | NA |
| Hunger AUC 3 meals | NA [NA; NA] | NA [NA; NA] | NA [NA; NA] | NA [NA; NA] | NA | NA [NA; NA] | NA |
| Hunger AUC breakfast | NA [NA; NA] | NA [NA; NA] | NA [NA; NA] | NA [NA; NA] | NA | NA [NA; NA] | NA |
| Hunger AUC lunch | NA [NA; NA] | NA [NA; NA] | NA [NA; NA] | NA [NA; NA] | NA | NA [NA; NA] | NA |
| Hunger AUC dinner | NA [NA; NA] | NA [NA; NA] | NA [NA; NA] | NA [NA; NA] | NA | NA [NA; NA] | NA |
| Fullness AUC 3 meals | NA [NA; NA] | NA [NA; NA] | NA [NA; NA] | NA [NA; NA] | NA | NA [NA; NA] | NA |
| Fullness AUC breakfast | NA [NA; NA] | NA [NA; NA] | NA [NA; NA] | NA [NA; NA] | NA | NA [NA; NA] | NA |
| Fullness AUC lunch | NA [NA; NA] | NA [NA; NA] | NA [NA; NA] | NA [NA; NA] | NA | NA [NA; NA] | NA |

| | | | | | | | |
|----------------------------------|-------------|-------------|-------------|-------------|----|-------------|----|
| Fullness AUC dinner | NA [NA; NA] | NA [NA; NA] | NA [NA; NA] | NA [NA; NA] | NA | NA [NA; NA] | NA |
| Desire AUC 3 meals | NA [NA; NA] | NA [NA; NA] | NA [NA; NA] | NA [NA; NA] | NA | NA [NA; NA] | NA |
| Desire AUC breakfast | NA [NA; NA] | NA [NA; NA] | NA [NA; NA] | NA [NA; NA] | NA | NA [NA; NA] | NA |
| Desire AUC lunch | NA [NA; NA] | NA [NA; NA] | NA [NA; NA] | NA [NA; NA] | NA | NA [NA; NA] | NA |
| Desire AUC dinner | NA [NA; NA] | NA [NA; NA] | NA [NA; NA] | NA [NA; NA] | NA | NA [NA; NA] | NA |
| Consumption AUC 3 meals | NA [NA; NA] | NA [NA; NA] | NA [NA; NA] | NA [NA; NA] | NA | NA [NA; NA] | NA |
| Consumption AUC breakfast | NA [NA; NA] | NA [NA; NA] | NA [NA; NA] | NA [NA; NA] | NA | NA [NA; NA] | NA |
| Consumption AUC lunch | NA [NA; NA] | NA [NA; NA] | NA [NA; NA] | NA [NA; NA] | NA | NA [NA; NA] | NA |
| Consumption AUC dinner | NA [NA; NA] | NA [NA; NA] | NA [NA; NA] | NA [NA; NA] | NA | NA [NA; NA] | NA |
| Fasting ghrelin | NA [NA; NA] | NA [NA; NA] | NA [NA; NA] | NA [NA; NA] | NA | NA [NA; NA] | NA |
| Ghrelin AUC of 3 meals | NA [NA; NA] | NA [NA; NA] | NA [NA; NA] | NA [NA; NA] | NA | NA [NA; NA] | NA |
| Ghrelin AUC of breakfast | NA [NA; NA] | NA [NA; NA] | NA [NA; NA] | NA [NA; NA] | NA | NA [NA; NA] | NA |
| Ghrelin AUC of lunch | NA [NA; NA] | NA [NA; NA] | NA [NA; NA] | NA [NA; NA] | NA | NA [NA; NA] | NA |
| Ghrelin AUC of dinner | NA [NA; NA] | NA [NA; NA] | NA [NA; NA] | NA [NA; NA] | NA | NA [NA; NA] | NA |
| Fasting GLP1 | NA [NA; NA] | NA [NA; NA] | NA [NA; NA] | NA [NA; NA] | NA | NA [NA; NA] | NA |
| GLP1 AUC of 3 meals | NA [NA; NA] | NA [NA; NA] | NA [NA; NA] | NA [NA; NA] | NA | NA [NA; NA] | NA |
| GLP1 AUC of breakfast | NA [NA; NA] | NA [NA; NA] | NA [NA; NA] | NA [NA; NA] | NA | NA [NA; NA] | NA |
| GLP1 AUC of lunch | NA [NA; NA] | NA [NA; NA] | NA [NA; NA] | NA [NA; NA] | NA | NA [NA; NA] | NA |
| GLP1 AUC of dinner | NA [NA; NA] | NA [NA; NA] | NA [NA; NA] | NA [NA; NA] | NA | NA [NA; NA] | NA |

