| Treatment 
 - eCR (30% calorie restriction, 8am – 4pm); - dCR (30% calorie restriction, 12pm – 8pm); - CR (30% calorie restriction, 8am-8pm); Control group | |
| ESTIMAND | ANALYSIS |
| Target population 
 - Men and women with obesity and elevated fasting blood glucose | Analysis set 
 - All randomized - Initiated diet |
| Variable 
 - Glucose AUC over 3 meals (breakfast, lunch, dinner). | Outcome measure 
 - Blood glucose AUC - Measured at 0,30,60,120 post-meal - Averaged over three meals |
| Handling of inter-current events 
 1. Death (while on treatment strategy, or “while alive”) 2. Discontinuation: other reason (while on treatment strategy) 3. Discontinuation: dislike of diet (treatment policy strategy) 4. Lost-to-follow-up no reason provided (treatment policy strategy) | Handling of missing data 
 1. Death believed not to be relevant for this study, included for completeness. 2. All individuals discontinuing early will (i) be invited to attend the week 6 assessment for fasting bloods and body weight only, (ii) asked whether the reason for discontinuation is due to allocated diet. 3. Missing-at-random will be assumed for individuals who do not specify whether discontinuation was due to diet, or when the reason was not due to the diet. 4. For individuals who discontinued due to the diet a missing-not-at-random assumption will be made, assuming zero adherence after discontinuation, and conditional on adherence missing-at-random assumed to impute week 8 outcomes. |

| | |
|---|--|
| | 5. Imputation is by treatment group with individuals imputed in the groups they were allocated to. |
| Population level summary measure 
 - Mean between group differences in baseline adjusted log-transformed (within-individual) mean post-meal glucose AUC, of the time-restricted groups versus the control (non time-restricted) group. | Analysis approach 
 - Group differences of log transformed mean post-prandial AUC will be estimated using a single linear regression with a treatment (three levels) and baseline log transformed mean post-prandial glucose AUC and stratification factors (sex and fasting plasma glucose). |

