A secondary, complete-case sensitivity analysis will be performed for the analysis of the primary outcome and secondary efficacy outcomes in this analysis individuals with both baseline and week 8 assessments will only be included for each analysis.

As additional analysis will explore the treatment effects within subjects who were adherent to the protocol using data collected with the MyCircadianClock app plus the dietary checklists. This analysis will be reported in a secondary mechanistic publication of this study.

STATISTICAL METHODS

Primary Outcome

The primary analysis of the primary outcome is a covariate adjusted linear regression of the differences in PP glucose log AUC at 8 weeks from baseline. Covariates included will be treatment (three groups), baseline glucose log AUC, sex and fasting plasma blood glucose (as a continuous linear variable). Visual inspection of the residual distribution will be used to determine if assumptions of normality and the absence of a variance-mean association appear to be violated. If assumptions appear violated a generalized linear models will be considered with differing link functions will be considered and presented as sensitivity analyses. Given the limited sample size, no subgroup analyses are planned.

This analysis will be performed in all randomized individuals with individuals using multiple imputation using chained equations within treatment groups and combined using Rubin's rules. The variables used in the multiple imputation are age and sex; baseline and week 8 assessments of weight, PP glucose and insulin AUC (per meal), fasting glucose, fasting insulin and HbA1c; and the self-reported adherence over the 8 weeks and reason for discontinuation (related/unrelated to diet) if applicable. All concentrations will be imputed on the log scale, with the 3-meal mean of PP glucose and insulin AUC being calculated on the original scale after a back-transformation. Compliance will be imputed as per the intercurrent event strategies and the average compliance calculated over each period. Imputation will use multiple chained equations (*mice* R package), details of which are attached separately (file: *OMIT – Imputation code 2024-12-18.r*).

Secondary Efficacy Outcomes

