The four secondary efficacy outcomes used in the multiple imputation of the primary outcome will be assessed using the same methodology as for the primary outcome, i.e. covariate adjusted linear regressions with multiple imputation for missing data.

Exploratory Outcomes

Exploratory outcomes will also be analysed using baseline and stratification factor adjusted linear regressions. The weight and PP glucose and insulin meal specific analyses will be performed in the imputed data sets. All other outcomes will be analysed using complete case data sets.

Safety Outcomes

Summaries, for all adverse events and for those events believed to be related to the intervention, will be reported. In both cases, if an individual has experienced the adverse event on multiple occasions, only the event with the maximum grade will be reported.

When there are at least four individuals who experience a particular adverse event, a Fisher exact test will be conducted comparing the rates of occurrence (irrespective of grade) between the two intervention groups. No adjustments for multiple testing will be performed.

[figure not shown]
STUDY SUMMARY TABLES

Descriptive Statistics: A CONSORT flow chart will present all individuals screened through to randomization and week 8 assessment will be presented (Figure 2). The number of individuals who discontinue their allocated intervention and/or withdraw from the study, the week and reason for discontinuation will be reported.

Descriptive summary statistics will be reported for baseline characteristics of all individuals who were randomized. In addition to baseline glycemia indices we will report on age, sex, menopausal status, AUSDRISK, body composition, markers of CVD risk, sleep, activity and appetite measures. For continuous variables means, standard deviations, medians and ranges will be reported, and for discrete variables frequency and percentages will be reported. No demographic summary statistics were collected for the screened cohort.

Results tables presenting the analyses of the primary, secondary and exploratory outcomes are presented in Appendix A.

Figure 2: CONSORT flow chart of OMIT study.

REFERENCES

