## Reformat adherence so that 0 = worst adherence.
```

```
imp.data$adher.w2 <- 5 - as.numeric(imp.data$adher.w2)
```

```
imp.data$adher.w4 <- 5 - as.numeric(imp.data$adher.w4)
```

```
imp.data$adher.w8 <- 5 - as.numeric(imp.data$adher.w8)
```

```

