## Calculate mean adherence
```

```
imp.data$adherence <- (as.numeric(imp.data$adher.w2) + as.numeric(imp.data$adher.w4) + 2*as.numeric(imp.data$adher.w8))/4
```

```

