## Set adherence to "Strongly Disagree" (ie 0) when due to diet and after drop-out week
```

```
for (id. in temp.data$id[temp.data$drop.out == 'Diet' & !is.na(temp.data$drop.out)]) {
```

```
week. <- temp.data$week.drop[temp.data$id == id.]

if (week. < 2) temp.data$adher.w2[temp.data$id == id.] <- 0

if (week. < 4) temp.data$adher.w4[temp.data$id == id.] <- 0

if (week. < 8) temp.data$adher.w8[temp.data$id == id.] <- 0

rm(week.)

}; rm(id.)

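### Table A5 compares adherence on complete cases, which leaves out the diet-related discontinuers whom the plan elsewhere scores zero; the contrast then favours any arm with more such discontinuation

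*SAP*

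**What the plan says.** Study Outcomes names self-reported adherence over the eight weeks as a compliance outcome. Appendix A carries an Adherence row in Table A5, with estimates per arm, two contrasts against control and a p-value for each. That table is captioned "Exploratory outcome analyses for outcomes not used in the multiple imputation of the primary outcome, ie complete case analyses". The Exploratory Outcomes section agrees on the analysis set: weight and the meal-specific glucose and insulin analyses use the imputed data, and "All other outcomes will be analysed using complete case data sets".

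The Primary Outcome section, however, lists among the imputation variables "the self-reported adherence over the 8 weeks and reason for discontinuation (related/unrelated to diet) if applicable". The estimand table imputes week 8 outcomes for those who stopped because of the diet by "assuming zero adherence after discontinuation". The imputation code carries this out on its working copy of the data, for example "if (week. < 8) temp.data$adher.w8[temp.data$id == id.] <- 0".

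In the un-imputed data the eight-week mean is "imp.data$adherence <- (as.numeric(imp.data$adher.w2) + as.numeric(imp.data$adher.w4) + 2*as.numeric(imp.data$adher.w8))/4". Under Handling of missing data, participants who stop early are asked back at week 6 for fasting blood samples and weighing only.

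**The concern.** Two things do not fit together. First, the appendix sorts exploratory outcomes by whether they enter the imputation: Table A4 if they do, Table A5 if not. Adherence enters it but sits in Table A5.

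Second, the complete-case rule selects on the outcome being compared. Stopping because of the diet is itself non-adherence, and those participants would normally be the ones without a complete score. The trial would then report a primary analysis that treats them as non-adherent after stopping and an adherence comparison that omits them. At stake is how a reader judges which eating schedule people could follow, since the row is tested between arms.

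**Working it through.** The plan gives no expected adherence value or SD, so there is no planned figure to reproduce. The check has two parts.

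**1. Tracing the variable through the SAP and its code**

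- Adherence is in the code's list of calculated variables, is a predictor in every week 8 imputation formula, and has its own imputation method. It is therefore used in the imputation, contrary to the Table A5 caption.
- The zeros after diet-related stopping are written only to `temp.data`, the copy passed to the imputation.
- The complete-case models shown in the code run on `imp.data`. There the mean is a plain sum over weeks 2, 4 and 8, so it is missing if any one rating is missing.
- Early discontinuers are not asked back for an adherence rating, so week 8 would normally be missing.

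**2. Size, as an illustration**

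Inputs from the SAP:
- 38 participants per arm (Pre-planned Sample size).
- Mean adherence = (w2 + w4 + 2 × w8)/4.
- Zero only for ratings due after a diet-related stop; ratings before it are kept.

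Assumptions:
- A 0–4 scale. The recoding "imp.data$adher.w8 <- 5 - as.numeric(imp.data$adher.w8") with the worst answer set to 0 implies this if the original codes run from 1 to 5.
- On-diet ratings of 3.0 in both arms.
- k diet-related discontinuers in one time-restricted arm and none in CR.

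Score q of one discontinuer:
- stops in week 1: (0 + 0 + 2 × 0)/4 = 0
- stops in week 3: (3 + 0 + 2 × 0)/4 = 0.75
- stops in week 5: (3 + 3 + 2 × 0)/4 = 1.50

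The complete-case mean is 3.00 in both arms, a difference of 0.00. With the plan's zeros the difference is −k × (3.0 − q)/38:

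| k of 38 | stop week 1 | stop week 3 | stop week 5 |
|---|---|---|---|
| 3 | −3 × 3.00/38 = −0.24 | −3 × 2.25/38 = −0.18 | −3 × 1.50/38 = −0.12 |
| 4 | −4 × 3.00/38 = −0.32 | −4 × 2.25/38 = −0.24 | −4 × 1.50/38 = −0.16 |

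On-diet ratings of 2.5 to 3.5 scale these in proportion, giving 0.10 (3 × 1.25/38) to 0.37 (4 × 3.5/38).

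Two contrasting cases:
- Equal diet-related stopping in both arms, with the same ratings and timing: the difference is 0 under either method, though both complete-case means are too high.
- Completers at 2.6 against 3.0 in CR, 3 discontinuers in week 3: complete case gives 2.6 − 3.0 = −0.40. With zeros, q = 2.6/4 = 0.65, the arm mean is (35 × 2.6 + 3 × 0.65)/38 = 2.446, and the difference is −0.55. Complete case shrinks the gap without removing it.

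**The case against.** A reader might infer that the less tolerable arm will look as adherent as the others. The documents do not support that. It needs equal adherence among completers together with unequal diet-related stopping, and the SAP predicts neither.

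A reader might also say that the omitted participants have known lowest values. They do not: zero adherence is a missing-not-at-random assumption made for imputation, not a measurement. A summary of observed ratings is therefore not false; it answers a narrower question.

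A larger size is tempting too. With 10% of an arm stopping and completers at 3.0 to 3.5, zero for all eight weeks gives 0.10 × 3.0 = 0.30 to 0.10 × 3.5 = 0.35. That needs every one of them to stop before week 2, because the plan's code keeps earlier ratings.

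Other points on this side have weight:
- No code for the Adherence row is shown, and adherence is not in the list of analysed variables. The mechanism is read from the caption, the Exploratory Outcomes text and the definition in `imp.data`. If available ratings were averaged instead, those stopping after week 2 would stay in, but still without the zeros.
- The SAP reports the number, week and reason of discontinuations, and eating-window adherence is assessed separately. This helps the reader but does not correct the Table A5 estimate or p-value.
- Using imputed adherence makes the test depend partly on the zero assumption and on the adherence imputation models, which have no intercept.

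**Conclusion.** The point holds in a limited form. Adherence is in the wrong table by the SAP's own sorting rule; this needs no assumption about the data. On the plain reading of the plan, early diet-related discontinuers would normally leave the comparison. Arm means are then overstated relative to the plan's own scoring, and the contrast is biased towards any arm with more such stopping.

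The illustrated size, about 0.12 to 0.32 points, rests on the assumed scale, an on-diet rating of 3.0, 3 or 4 discontinuers in one arm and none in CR. Without an SD, the documents do not show how much this would change the p-value. This is a compliance outcome in an exploratory table, outside the error-control scheme.

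**What to change.** - Move Adherence from Table A5 to Table A4. Analyse the eight-week mean in all randomised participants from the imputed data sets: zero after diet-related stopping, ratings before stopping kept, other gaps imputed as already planned.
- Adjust for the stratification factors only. Adherence has no baseline value, and the Covariate adjustment section asks for a baseline term only where one is appropriate.
- Keep the complete-case figure as a labelled descriptive or sensitivity row, with its n per arm.
- State in the text how adherence is scored after discontinuation.

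The cost is one moved row and one added model call, since imputed adherence is already produced by the code. The downside is that the estimate will depend partly on the zero-adherence assumption and will look less favourable; the retained complete-case row lets the reader see by how much.
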